	
APR-246 PO on Day 2. The primary purpose of the monotherapy cycle is to obtain peripheral blood for monotherapy PK and PD analyses following IV and PO administration of APR-246.
 
Patients will start treatment with APR-246 IV as a single agent administered on Day 1 of a single 7-day monotherapy cycle at the assigned cohort dose level, prior to Cycle 1 Day 1 of combination therapy. On Day 2 of the 7-day monotherapy lead-in period, patients will receive a single dose of APR-246 administered PO at the dose of 500 mg. After review of oral PK data from at least 6 patients, a decision can be made whether to increase the PO dose of APR-246 and/or administer APR-246 with a standard high-fat meal to investigate, respectively, dose linearity in PK and/or the effect of food on oral absorption of APR-246. Dose escalation of the oral dose or switching to administration with food will be determined by PK to ensure that the APR-246 exposure levels after oral dosing do not exceed the exposure levels after IV administration in terms of C_{max} and AUC.
 
Combination Treatment
 
After the APR-246 monotherapy lead-in, study treatment will consist of APR-246 administered as an IV infusion, at the same assigned dose that was used during the monotherapy lead-in period, once weekly, on Days 1, 8 and 15 of each cycle, concurrently with venetoclax for the 5-week ramp-up at the dose of 20 mg during Week 1, 50 mg during Week 2, 100 mg during Week 3, 200 mg during Week 4, and 400 mg during Week 5. Beginning Cycle 2 Day 1, venetoclax will be administered at 400 mg (or tolerable dose following 5-week ramp up) PO daily. IV rituximab will be initiated at 375 mg/m² on Cycle 2, Day 2 and then administered at 500 mg/m² on Day 2 of Cycles 3-7. After 6 cycles of treatment with APR-246 in combination with venetoclax + rituximab, APR-246 + venetoclax will continue to be administered starting at Cycle 8 for up to a total of 24 cycles. The safety assessment (DLT) period will occur in the monotherapy lead-in and throughout Cycles 1, 2, and 3 of combination treatment.
 
Patients with RT will receive APR-246 administered IV as the assigned cohort dose with standard doses of venetoclax and rituximab. Dose escalation will proceed in a standard 3 + 3 dose escalation design.
 
Patients who miss >25% of APR-246 doses for a nonmedical reason (patient's preference) or noncompliance will be replaced.
 
Patients who receive at least 3 cycles of study treatment at the assigned dose of APR-246 may proceed to the next dose level of APR-246 that has been demonstrated as safe and tolerable by the DRT in at least 3 patients, provided the dose increase is considered to be in the patient's best interest by the Investigator.
 
Responses will be assessed according to response criteria for RT (Appendix V) via blood, BM, and imaging (positron emission tomography [PET]/computed tomography [CT]). Response assessments are to be performed every 3 cycles and PET-CT scanning is recommended. For patients who achieve CR, imaging may be omitted, and minimal residual disease (MRD) assessment will be completed using flow cytometry and/or molecular techniques from the BM and/or peripheral blood.

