Upon determination of the pharmacologically active dose or MTD, or when the maximally intended dose is reached, up to 10 additional patients may be enrolled at this dose level to confirm the assessment and to collect additional safety, PK and PD data to aid in determining the recommended dose of APR-246 in combination with venetoclax and rituximab.

Table 3. APR-246 Dose Levels

Dose Modification	APR-246 Dose
Dose Level 1	APR-246 1.5 g/day 0.5 g (for first 45 minutes) + 1.0 g (for 5 hours 15 minutes)
Dose Level 2	APR-246 3.0 g/day 1.0 g (for first 45 minutes) + 2.0 g (for 5 hours 15 minutes)
Dose Level 3	APR-246 4.0 g/day 1.33 g (for the first 45 minutes) + 2.66 g (for 5 hours 15 minutes)

Prior to initiation of study treatment with APR-246 administered IV in combination with venetoclax and rituximab (during treatment cycles 2-7), patients will receive APR-246 alone on Day 1 and Day 2 of the 7-day monotherapy lead-in period, during which PK and PD of APR-246 following IV and PO administration will be evaluated. On Day 1 of the monotherapy lead-in period, APR-246 will be administered IV at the assigned cohort dose. On Day 2, APR-246 will be administered PO at the dose of 500 mg. This dose may be increased based on emerging PK data to determine dose linearity after oral dosing. Patients will be required to fast for at least 10 hours prior to APR-246 PO administration. Furthermore, a sub-group of patients may receive an oral dose of APR-246 in combination with a standard high-fat meal to determine the effect of food on APR-246 absorption.

Additional dose levels may be explored if warranted based on emerging DLT, safety, PK, and/or PD data. In addition, patients who have received at least 3 cycles of therapy at the assigned dose cohort level may advance to the next higher dose level once the next higher dose level has been declared safe by the DRT.

Responses will be assessed according to response criteria for RT ([Appendix V](#)) via blood, BM, and imaging (positron emission tomography [PET]/computed tomography [CT]). Response assessments are to be performed every 3 cycles and PET-CT scanning is recommended. For patients who achieve CR, imaging may be omitted, and minimal residual disease (MRD) assessment will be completed using flow cytometry and/or molecular techniques from the BM and/or peripheral blood.

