5.1.5 Recommended Dose of APR-246

The recommended dose of APR-246 in combination with venetoclax and rituximab represents the dose of APR-246 at or below the maximum intended dose, or the MTD, that results in the greatest apoptosis of circulating malignant cells in the monotherapy cycle.

The MTD of APR-246 will be defined as the dose at which <2 out of 6 patients experience DLT during the defined safety assessment period after administration of APR-246 in combination with venetoclax and rituximab. Up to 10 additional patients may be enrolled at the MTD, and at prior dose levels, to confirm the confidence at that dose level.

A DRT consisting of the Medical Monitor, Site Principal Investigators, and other clinical research personnel that the Sponsor may deem appropriate, will hold Data Review Meetings (DRMs) on an

interim basis at a frequency dependent on study accrual. At these meetings, the DRT will review any AEs, DLTs, and any available PK and PD data and make recommendations regarding the optimal dose of APR-246. All accumulated safety data will be discussed during DRMs. The optimal dose of APR-246 will be based upon the MTD and upon all accumulated safety data, PK/PD data, and preliminary efficacy data.

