- e. Physical exam and vital signs (including blood pressure, heart rate, respiration rate and temperature) are completed for safety purposes and clinically significant items are recorded as AEs where appropriate. Vital signs are collected prior to APR-246 infusion, 2 hours into infusion and at EOI (± 30 minutes at all time points). On Day 2 of the APR-246 monotherapy lead-in period, vital signs are collected prior to PO administration of APR-246, and then 2 hours and 6 hours after APR-246 administration. For patients with palpable lymphadenopathy and/or organomegaly, 2 dimensional measurements of lymph nodes and measurements of liver/spleen size (below costal margin) may be included as part of each physical examination as clinically indicated.
- f. Study treatment will consist of APR-246 at assigned dose level administered once weekly, on Days 1, 8 and 15 of each 28-day cycle. On Day 2 of the monotherapy lead-in period, a single dose of APR-246 will be administered PO.
- g. Venetoclax is given PO at the dose of 20 mg during Week 1, 50 mg during Week 2, 100 mg during Week 3, 200 mg during Week 4, and 400 mg during Week 5 and thereafter. Each dose should be given once daily at approximately the same time every day, with a meal and water. At the discretion of the treating Investigator, patient may be hospitalized prior to administration of the first dose of venetoclax (20 and 50 mg) and continuing for 24 hours after.
- h. Rituximab will be initiated IV, following the 5-week venetoclax dose ramp-up, at 375 mg/m^2 on Cycle 2, Day 2 ($+3$ days) and 500 mg/m^2 on Day 2 ($+3$ days) of Cycles 3-7. After 6 cycles of treatment with APR-246 + venetoclax + rituximab, APR-246 and venetoclax will continue to be administered in Cycle 8 and beyond for up to 24 cycles.
- i. Responses will be assessed every 3 cycles starting at Cycle 4 on Day 1 (± 7 days) according to Lugano response criteria via PET/CT imaging, blood, and BM. For patients who achieve CR, imaging may be omitted, and MRD assessment will be completed using flow cytometry and/or molecular techniques.
- j. Hematology must include complete blood count with differential. Hematology test should be completed before and after APR-246 administration on Days 1 and 2 of the APR-246 monotherapy lead-in period, Day 3 of the lead-in period, and on Day 1 of Cycle 1 before and approximately 4 hours after APR-246 administration.

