8.0 STATISTICS

Continuous variables will be presented by n , mean, median, standard deviation and range (minimum and maximum), and categorical variables will be presented by count and percentage of patients as appropriate. Data will be presented by dose escalation cohort. All patient data, efficacy and safety data will be summarized and listed.

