8.1 Sample Size

A total of up to 48 evaluable patients will be included in the study.

Patients with RT will be enrolled and receive APR-246 at the assigned dose cohort level. Dose escalation will proceed in a 3 + 3 design. Cohorts will consist of 3-6 patients and 10 additional patients may be enrolled at the MTD. Approximately 6 + 6 + 6 (18) DLT evaluable patients will be enrolled. In the event Dose Level 3 is declared the MTD, up to 10 additional patients may be enrolled at Dose Levels 1 and 2 to gain additional safety, PK, and/or PD data to help define the recommended dose of APR-246 in this combination.

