8.3 Endpoints

8.3.1 Primary

1. PD analysis of circulating peripheral blood cells to determine effects of APR-246 on cellular viability and apoptosis.
2. Frequency of TEAEs and SAEs related to APR-246 in combination with venetoclax and rituximab therapy.
3. The highest tested dose of APR-246 with acceptable toxicity (the dose producing <33% of DLT).

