8.6 Safety

Safety data will be summarized for the safety population. These data will include AEs, laboratory parameters, electrocardiogram, and physical exam findings. AE terms will be coded using the Medical Dictionary for Drug Regulatory Activities (MedDRA)®, version 22.0 or higher. AEs will be summarized by SOC, preferred term, severity, and relationship to treatment. SAEs, deaths, and AEs leading to early discontinuation of study treatment will be summarized. Laboratory parameters will be summarized by maximum NCI-CTCAE version 5.0 severity grade and also by change from pre-treatment to scheduled time points using descriptive statistics. Laboratory parameter listings will include the normal ranges for each parameter. Each value will be classified as falling above, below, or within the normal range.

Only SAEs related to study screening procedures from the time of signing informed consent and AEs from the time of first dose of APR-246, throughout study enrollment, and up to 30 days after last dose of study treatment are to be collected. Data summaries will include only TEAEs, defined as events occurring at the start of APR-246 infusion in the monotherapy lead-in or Cycle 1, Day 1 up to and including 30 days after last dose of study treatment.

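### Patients may step up a dose level after three cycles, but the by-cohort safety tables, followed literally, would count their later adverse events under the lower starting dose

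*Combined protocol and SAP*

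**What the plan says.** **The permission.** The synopsis (Treatment Plan, Combination Treatment) states: "Patients who receive at least 3 cycles of study treatment at the assigned dose of APR-246 may proceed to the next dose level". It attaches two conditions. The DRT must have found the next level safe and tolerable in at least 3 patients, and the Investigator must judge the increase to be in the patient's best interest. Section 4.1 gives the same permission, saying that such patients "may advance to the next higher dose level once the next higher dose level has been declared safe by the DRT", but repeats neither the 3-patient minimum nor the best-interest condition.

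**The reporting unit.** Section 8.0: "Data will be presented by dose escalation cohort". It adds that all data will be summarized and listed.

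**The event window.** Section 8.6 summarizes TEAEs from the first APR-246 infusion "up to and including 30 days after last dose of study treatment". Nothing cuts the window at a dose increase.

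**The use of the data.** Section 8.3.1 makes "Frequency of TEAEs and SAEs related to APR-246" in the combination a primary endpoint. Section 5.1.5 bases the optimal dose on the MTD and "upon all accumulated safety data, PK/PD data, and preliminary efficacy data". Section 8.1 adds a provision for the case where the MTD turns out to be the top level: "up to 10 additional patients may be enrolled at Dose Levels 1 and 2 to gain additional safety, PK, and/or PD data". These patients are meant to inform the choice of dose.

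**What is absent.** Sections 8.2, 8.6 and 8.7 and the synopsis statistics never mention patients who move up. There is no table by dose at onset, no named listing of movers, and no statement on how response or time-to-event endpoints treat the move.

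**The concern.** A patient who starts at 1.5 g/day and moves to 3.0 g/day stays in the 1.5 g/day cohort for reporting. A toxicity that first appears at 3.0 g/day is then printed in the 1.5 g/day column. If toxicity rises with dose, the lower level looks more toxic than it is and the contrast between levels shrinks.

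The additional Dose Level 1 and 2 patients are the ones most open to this. Under Section 8.1 they enrol only after Dose Level 3 has been declared the MTD, so the level above them is already cleared. They are enrolled to sharpen the picture at the lower doses, yet each could leave that dose as soon as Cycle 3 ends.

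**Working it through.** **1. The plan's own total.** Three cohorts of 6, plus 10 at the MTD, plus 10 at each of Dose Levels 1 and 2 (Section 8.1): 18 + 10 + 20 = 48. This reproduces the stated maximum.

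**2. Who could move.** Patients starting below 4.0 g/day: 2 × (6 + 10) = 32 of 48, of whom 20 are additional patients. This is a ceiling. It needs Dose Level 3 to be the MTD, all optional places filled, and 6 rather than 3 patients in each lower cohort.

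**3. Earliest move.** Lead-in 7 days, Cycle 1 35 days, Cycles 2 and 3 28 days each: 7 + 35 + 28 + 28 = 98 days.
- Additional patients: from day 98, because the next level is already cleared.
- Escalation-cohort patients: the next level opens after their own DLT window and must then pass its own, so about 98 + 98 = day 196. Cycle 7 runs from day 183 to day 210, so this falls in Cycle 7. Section 5.1.4 gives the window as 91 days; on that figure the date is 2 × 91 = day 182, the end of Cycle 6. Both dates assume no gap in enrolment.

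**4. Dosing after a move.** IV doses through Cycle 3: 1 + 3 × 3 = 10. Cycles 4 to 24: 21 × 3 = 63.
- Move at day 98 and complete 24 cycles: 63/73 = 86% of doses above the cohort dose (upper bound).
- Move at day 98 and stop after Cycle 6: 9/19 = 47%.
- Escalation-cohort patient who moves at the start of Cycle 8 and completes 24 cycles: 17 × 3 = 51, and 51/73 = 70%.

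**5. How many reach these points (assumption).** Section 2.1 gives a median OS of 3 to 11 months. With exponential survival, S(t) = exp(−ln2 × t / median):

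| Day | Months | Median 3 | Median 11 |
|---|---|---|---|
| 98 | 3.22 | 48% | 82% |
| 196 | 6.44 | 23% | 67% |
| 686 (end of Cycle 24) | 22.5 | 0.5% | 24% |

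Of 20 additional patients, about 10 to 16 would be alive at day 98. Fewer would still be on treatment, and fewer still would move.

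**6. Effect of one event.** One patient whose first event follows a move changes the lower cohort's rate by 1/16 = 6.3 points, 1/6 = 16.7 points or 1/3 = 33.3 points. The last two apply to escalation cohorts without additional patients, which are subject to the later date in step 3.

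**7. Illustrative shift in a cohort's event rate (assumed inputs).** Let f be the fraction who move, a the share with the event before the move, c the later risk if they stay and b the later risk after moving. Shift = f(1 − a)(b − c). With a = 0.20 and c = 0.10:
- f = 0.25: b = 0.20 gives 2 points; b = 0.40 gives 6 points.
- f = 0.50: b = 0.20 gives 4 points; b = 0.40 gives 12 points.

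If movers are robust enough that b equals c, the shift is zero.

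**8. What comes before any move.** The DLT window closes at the end of Cycle 3, and Section 5.1.4 excludes later events from DLT status. PD samples are taken in the lead-in and on Cycle 1 Day 1 (Table 18). Neither can be altered by a move.

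**9. Response.** Table 17, footnote i: "Responses will be assessed every 3 cycles starting at Cycle 4 on Day 1". Table 17 lists 8 assessments, 7 of them after a day-98 move. Section 6.7 omits Cycle 16, which gives 6 of 7. Cutting response at the move would leave the earliest movers a single assessment.

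**The case against.** The strongest case against is that this is a table-layout omission in a descriptive phase 1 trial with no power calculation. Reporting by assigned cohort is a legitimate choice. The documents nowhere say in words that later events belong to the lower dose. Listings are promised (Section 8.0). Section 8.9 relates APR-246 AUC and Cmax to safety and efficacy, with sampling on Day 1 of each cycle from Cycle 3. Section 5.1.4 has later TEAEs reviewed across all cohorts, and the DRT sees all accumulated data. Dose reductions create the same mismatch in the other direction. The primary TEAE/SAE endpoint is not worded as a comparison between doses.

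Most of this stands as mitigation. It does not remove the gap: none of these provisions governs the cohort tables or sets an attribution rule before the data are seen. The point about reductions is an argument for a dose-at-onset table, which handles both directions.

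A reader might go further and infer that the MTD or the recommended dose is compromised. The documents do not support that. The MTD rests on DLTs through Cycle 3, and Section 5.1.5 defines the recommended dose by apoptosis in the monotherapy cycle. A reader might also take 32 of 48 patients or 86% of doses as the expected scale; both are ceilings. Nor does it follow that response should be cut at the move. The decision to move depends on how the patient is doing, and scheduled marrow assessments begin only at Cycle 7 (Section 6.7), so a cut could understate response at the lower dose.

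**Conclusion.** The concern holds for the attribution of TEAEs and SAEs by dose. Read literally, Sections 8.0 and 8.6 place post-move events in the lower starting-dose column. This touches the reporting of a primary endpoint and one input to the optimal-dose review in Section 5.1.5. It does not touch the 3 + 3 decisions.

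The size cannot be fixed from the documents, because the number who would move is not given. The 2 to 12 point range rests on assumed rates, and its direction requires later risk to be higher after a move than at the starting dose. The survival figures assume exponential survival at the quoted medians. This is a worthwhile, inexpensive improvement to the analysis text and not a flaw that endangers the trial.

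**What to change.** In Sections 8.0 and 8.6:

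- Keep the by-cohort tables.
- Add TEAE, SAE and exposure tables by APR-246 dose at onset (for exposure, the dose received). Give movers' post-move period its own column, and do not pool it with patients who started at that dose, because movers were selected for having completed three cycles.
- List each mover with date, old dose and new dose.

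In Section 8.7, keep CR rate, ORR, DOR, PFS and OS by assigned cohort with movers flagged, and show best response before the move only as a supportive summary. In Section 4.1, repeat the synopsis's two conditions for moving up.

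The cost is a few sentences and some extra table columns with small denominators. Sample size, dosing and timelines do not change. No new data are needed: doses given (Section 4.6) and adverse event start dates (Table 17, footnote r) are already recorded.

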1.0 GENERAL INFORMATION

1.1 Protocol Number and Title of the Study

Protocol No. A20-11197

Protocol Title: Phase 1 Study of APR-246 in Combination with Venetoclax and Rituximab Therapy in Patients with Richter's Transformed Non-Hodgkin's Lymphomas

2.0 BACKGROUND INFORMATION

2.1 Disease Background

Non-Hodgkin's lymphomas (NHL) are lymphoid malignant neoplasms with diverse biological and clinical behavior, variously derived from the clonal expansion of B cells, T cells, natural killer cells or precursors of these cells.

Chronic lymphocytic leukemia (CLL) is one of the most common types of B-cell NHL, characterized by a progressive accumulation of functionally incompetent monoclonal lymphocytes¹. The incidence rates among men and women in the United States (US) are approximately 6.75 and 3.65 cases per 100,000 population per year, respectively^{2,3}.

CLL is associated with a highly heterogeneous disease course, with some patients surviving for more than 10 years without needing treatment, and others experiencing rapid disease progression and poor outcomes despite effective chemoimmunotherapy (CIT)⁴⁻⁸. This heterogeneity is partly explained by the diverse genetic aberrations identified in approximately 80% of CLL patients⁹⁻¹², including a deletion in chromosome 13q14.3 (del(13q)), del(11q), del(17p) and trisomy 12, associated with an intermediate prognosis. Del(13q) is the most common chromosomal alteration, evident in >50% of patients, and is associated with favorable prognosis¹³. Del(17p) is found in 7% of patients and is associated with loss of the tumor suppressor gene *TP53*¹⁴, whereas del(11q) is found in 18% of patients

and is often associated with alterations in ATM; each of these chromosomal alterations is associated with adverse clinical outcome^{9,15}. Deletions in chromosome 17p [del(17p)] resulting in loss of the *TP53* gene, which encodes the tumor-suppressor protein p53, belong to the strongest prognostic and predictive markers guiding treatment decisions in CLL, and are associated with markedly decreased survival and impaired response to CIT¹⁶⁻²⁰. CLL patients with alterations of *TP53* have inferior outcomes with all CLL directed therapies, in particular CIT combinations, and these patients (if fit) were historically considered for referral for allogeneic hematopoietic stem cell transplantation in first remission²¹⁻²⁵. New small-molecule inhibitors that are efficacious in patients harboring *TP53* mutations are now available, including the BTK inhibitors ibrutinib and acalabrutinib, the phosphatidylinositol 3-kinase inhibitors idelalisib and duvelisib, and the B cell lymphoma-2 (Bcl-2) inhibitor venetoclax²⁶⁻³⁴.

[figure not shown]
Despite the introduction of targeted agents, 5-10% of previously treated CLL patients undergo transformation into high-grade lymphoma, a condition known as Richter's transformed NHL (RT). These patients typically present with an aggressive disease course and have poor response to traditional chemotherapy used to treat de novo diffuse large B-cell lymphoma and similar or shorter overall survival (OS) (median 3-11 months)^{35,36}. Based on clonal relationship of large cell component to CLL, 2 distinct subtypes could be identified: clonally-related RT which carries a worse outcome, and clonally-unrelated RT where the outcomes are similar to de novo diffuse large B-cell lymphoma³⁷. Specific risk factors for the development of RT in a patient with CLL have yet to be identified; however, *TP53* disruption, c-MYC abnormalities, unmuted immunoglobulin heavy chain <2%, non-del13q cytogenetics, CD38 gene polymorphisms, stereotypy, and VH4-39 gene usage may predispose to RT^{35,37,38}. The CLL-International Prognostic Index aids in predicting time to first therapy among previously untreated patients³⁸. The prognosis of patients with RT generally is poor, particularly for those who are heavily pretreated for CLL and/or who have transformation involving lymphocytes that are clonally related to the underlying CLL³⁹.

There is no standard of care for patients with RT, which represents a disease with unmet medical needs. Development of rituximab-containing intensive chemotherapy regimens and chemo-immunotherapy regimens have improved response rates but have not clearly affected long-term outcomes³⁵. CIT remains the treatment of choice, though the outcomes remain suboptimal, with the median survival of less than 1 year.

